#### **7.4.2 Drug exposure and dose modification**

The drug exposure in the two groups is described using mean, standard deviation, maximum, minimum, and median.

The treatment interruption and dose modification during the trial are summarized.

The duration of drug exposure, actual dose intensity, and relative dose intensity of apatinib and placebo are summarized using mean, standard deviation, median, maximum, and minimum.

The specific definition rules of derived variables for the study drugs apatinib and placebo are shown in Appendix 3.

#### **7.4.3 Vital signs**

Measured values and their changes before and after treatment are described using mean  $\pm$  standard deviation, maximum, minimum, and median.

#### **7.4.4 Laboratory test parameters**

Hematology, blood biochemistry, and AFP: Measured values and their changes before and after treatment are described using mean  $\pm$  standard deviation, maximum, minimum, and median. Normal and abnormal changes after treatment are described in a shift table.

Urinalysis: Normal and abnormal changes after treatment are described using a shift table.

Stool routine: Normal and abnormal changes after treatment are described using a shift table.

The proportion of subjects with "abnormalities with clinical significance" will be presented, where the clinical significance of the abnormality is judged by the investigator.

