3.2 Inclusion Criteria

Inclusion criteria:

1. Age: ≥ 18 years old;
2. Patients strictly meeting the clinical diagnostic criteria in "Guideline on Diagnosis and Treatment for Primary Liver Cancer" (2011 Edition) or with histologically or cytologically confirmed recurrent/metastatic HCC, unsuitable for palliative surgery or radiation therapy, with at least one measurable lesion (must be ≥ 10 mm in longest diameter by spiral CT or ≥ 15 mm in shortest diameter for enlarged lymph nodes, as per RECIST 1.1, as shown in Annex 1);
3. Patients with HCC refractory or intolerant to systematic chemotherapy (with oxaliplatin, alone or in a therapeutic combination) and/or molecular targeted therapy with sorafenib;

Note: Definition of treatment failure: disease progression during treatment or relapse after treatment is completed (must have received ≥ 1 cycle of systemic chemotherapy with oxaliplatin (or plus other drugs) or ≥ 14 days of molecular targeted therapy with sorafenib);

Definition of intolerance: Grade $\geq IV$ hematological toxicity or Grade $\geq III$ non-hematological toxicity or Grade $\geq II$ major organ injury such as the heart, liver, or kidneys during treatment.

4. The interval between the last systemic treatment failure (with treatment discontinued) and the enrollment (time of signing the informed consent form) was ≥ 2 weeks, and the adverse event(s) had basically returned to normal (NCI-CTCAE \leq Grade I);
5. Child-Pugh score: Class A or Class B (≤ 7); the Child-Pugh scoring system is shown in Appendix 2;
6. BCLC staging: B-C (the "Barcelona Clinic Liver Cancer (BCLC) Staging System, 2010" is shown in Appendix 3);
7. ECOG PS of 0–1 within 1 week before enrollment, as shown in Appendix 4;
8. Expected survival ≥ 12 weeks;
9. HBV DNA < 2000 IU/mL (10^4 copies/mL);
10. Major organs must function normally, meeting the following criteria:
 - (1) Hematology: (without blood transfusion, G-CSF, or medication within 14 days prior to screening)
 - d. HB ≥ 90 g/L;
 - e. ANC $\geq 1.5 \times 10^9$ /L;
 - f. PLT $\geq 80 \times 10^9$ /L;
 - (2) Biochemistry: (no ALB transfusion within 14 days)
 - e. ALB ≥ 29 g/L;
 - f. ALT and AST $< 5 \times$ ULN;
 - g. TBIL $\leq 1.5 \times$ ULN;
 - h. Creatinine $\leq 1.5 \times$ ULN;
- (Only one of the two items, albumin or bilirubin, has a Child-Pugh score of 2)

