For the comparison of 3-, 6-, and 12-month PFS rates, objective response rate (ORR), disease control rate (DCR), the percentage of patients with stable disease (SD) of ≥ 4 weeks (confirmed SD in particular), and 6- and 12-month mortalities, CMH- χ^2 tests with and without central stratification are used to compare the efficacy between the two groups. In addition, the 95% confidence interval of the difference between the two groups is also calculated. Based on the product limit method and the actual condition of the data, 25%, 50% (median) and 75% of PFS and TTP, as well as PFS and OS at different time points after the start of treatment, are calculated and the endpoints are compared between the two groups using the Log-Rank test.

- Safety analysis: Descriptive statistical analysis will be mainly used. The AEs and SAEs, treatment-related AEs and SAEs, and AEs and SAEs of special interest (e.g., hypertension, proteinuria, and hand-and-foot syndrome) are listed and summarized. If necessary, the incidence and severity of AEs and SAEs between different groups are compared using Fisher's exact test. For laboratory results, the cases in which the pre-treatment values are normal but the post-treatment values are abnormal will be described, and the relationship between the abnormal changes and the investigational drug will be evaluated.

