## 4 SAFETY ENDPOINTS

Safety evaluation parameters include vital signs, laboratory measurements, adverse events (AEs), serious adverse events (SAEs), treatment-related AEs and SAEs, and AEs specific to this type of drugs (e.g., hypertension, proteinuria, and hand-and-foot syndrome); judged per NCI-CTCAE V4.0.

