### 4.1 Adverse Events

AEs, treatment-related adverse events (TRAEs), and SAEs that have occurred during the study period.

An AE refers to any untoward medical occurrence in a clinical investigation subject and which does not necessarily have a causal relationship with the treatment. AEs include but are not limited to: laboratory abnormalities; clinically significant symptoms and signs; allergies;

According to the needs of management, safety monitoring (reporting of AEs or SAEs) should be performed from the signing of the informed consent form by the subject to 28 days after the last dose.

Treatment-related AEs (TRAEs): All toxicities and unintentional reactions to a drug associated with any dose should be considered as Treatment-related AEs (TRAEs). Treatment-related AE means that a potential causal relationship between the drug and AE is at least reasonable, which means that the relationship cannot be excluded. The potential relationship between an AE and the investigational drug is assessed with 5 grades of causality: definitely related, probably related, possibly related, unlikely related, and not related. Events that are assessed to be "definitely related", "probably related", and "possibly related" are considered related to the investigational drug. When calculating the incidence of Treatment-related AEs, the total number of these three categories is used as the numerator and the total number of subjects in safety set is used as the denominator.

A SAE refers to a medical occurrence during the clinical trial that results in hospitalization, prolonged hospitalization, disability, incapacity, life threatening events or death, or congenital malformation. The following unexpected medical events are included:

- Events resulting in death;

- Life-threatening events (defined as events where the subject is at immediate risk of death at the time of the onset);
- Events resulting in hospitalization or prolonged hospitalization;
- Events resulting in permanent or serious disability/incapacity;
- Congenital anomalies or birth defects;
- Overdose;
- Pregnancy during the clinical trial.

Criteria for other SAEs specified in the protocol:

- Cardiac insufficiency — defined as any symptom or sign of reduced LVEF (NCI CTCAE Grade 3), or LVEF reduced by  $\geq 20\%$  from baseline and below the lower limit of normal (or reduced to  $< 50\%$ ).

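### No laboratory shift table by CTCAE grade is specified, so a subject's worsening from an abnormal baseline does not show in the planned shift tables

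*SAP*

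**What the plan says.** SAP 7.4.4 plans three laboratory outputs.

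- Continuous summaries for hematology, biochemistry and AFP: "Measured values and their changes before and after treatment are described using mean", together with standard deviation, maximum, minimum and median.
- Shift tables for the same parameters: "Normal and abnormal changes after treatment are described in a shift table". Urinalysis and stool routine get the same two-category shift, and for them it is the only tabulation named.
- The proportion of subjects with an abnormality that the investigator judges clinically significant.

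Protocol 12.3, under safety analysis, says of laboratory results that "the cases in which the pre-treatment values are normal but the post-treatment values are abnormal will be described".

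Inclusion criterion 10 in Protocol 3.2 opens with "Major organs must function normally, meeting the following criteria", but the limits that follow reach outside the normal range. They admit "ALT and AST $< 5 \times$ ULN", total bilirubin and creatinine up to 1.5 x ULN, albumin from 29 g/L, hemoglobin from 90 g/L and platelets from 80 x 10^9/L.

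SAP section 4 lists laboratory measurements among the safety parameters and closes the list with "judged per NCI-CTCAE V4.0". SAP 4.1 adds that "AEs include but are not limited to: laboratory abnormalities".

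**The concern.** A two-category shift table is informative only for subjects who start normal. This protocol expects some who do not: it sets liver-test entry ceilings above the ULN and allows albumin or bilirubin to score 2 on Child-Pugh. For those subjects the table cannot separate no change from severe worsening.

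The SAP also names a grading standard for laboratory measurements and then specifies no laboratory table that uses it. At stake is a description by arm, drawn from measured values and independent of AE reporting, of how many subjects had liver tests or blood counts that worsened, and by how much.

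**Working it through.** There is no stated figure to reproduce. The check sets the table definition against the entry limits and the protocol's action limits, and then looks at scale.

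**Step 1: what two categories can show.** Classify each value as N (at or below ULN) or A (above ULN).

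| ALT, baseline to post-baseline (x ULN) | Cell | Visible as a shift? |
|---|---|---|
| 0.9 to 1.1 | N to A | Yes |
| 1.2 to 4 | A to A | No |
| 3 to 9 | A to A | No |
| 4.9 to 20 | A to A | No |

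A trivial crossing of the ULN counts as a shift; a threefold rise from 3 to 9 x ULN does not.

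**Step 2: entry limits against action limits.** Protocol 7.2.6 and the paragraph that follows it act on ALT > 5 x ULN with total bilirubin > 2 x ULN, on ALT > 8 x ULN, and on ALT > 5 x ULN lasting more than 2 weeks. From an entry ALT of 4.9 x ULN, 8 x ULN is a factor of 8/4.9 = 1.63 away. From an entry bilirubin of 1.5 x ULN, 2 x ULN is a factor of 2/1.5 = 1.33 away. An eligible subject can therefore cross these limits without leaving the abnormal-to-abnormal cell.

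**Step 3: whether another planned output counts these subjects from laboratory values.**

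- Summaries of change: a mean dilutes a severe minority, and a maximum shows one value, not how many subjects.
- Clinical-significance proportion: an investigator's judgement, not a grade.
- AE severity (SAP 7.4.1): worst severity per subject, but only for findings reported as AEs.
- SAEs: ALT > 5 x ULN with bilirubin > 2 x ULN is a protocol-defined SAE (Protocol 11.1.3, SAP 4.1). ALT > 8 x ULN alone is not in that list.

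None tabulates subjects by grade, or by multiple of ULN, from the laboratory data.

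**Step 4: scale, for illustration only.** Protocol Table 6 gives Grade III–V events in the phase II 750 mg group: transaminases 7/51 = 13.7%, bilirubin 8/51 = 15.7%. With 390 subjects randomized 2:1, the apatinib arm has 390 x 2/3 = 260.

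- Transaminases: 260 x 7/51 = 35.7
- Bilirubin: 260 x 8/51 = 40.8

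The share with an abnormal baseline is not in the documents. If it were 30% to 70%, and worst grade were independent of baseline status (both are assumptions), the abnormal-to-abnormal cell would hold:

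- Transaminases: 35.7 x 0.3 = 10.7 to 35.7 x 0.7 = 25.0 subjects
- Bilirubin: 40.8 x 0.3 = 12.2 to 40.8 x 0.7 = 28.5 subjects

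The phase II figures are AE counts, so this indicates how many subjects the shift table might fail to distinguish. It does not show how many would go unreported.

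**The case against.** The strongest reply is that the shift table is one output among several. The sentence just before it in SAP 7.4.4 plans values and changes with their range. Laboratory abnormalities are AEs in both documents, with no condition that the baseline be normal. Protocol 11.2 has AEs graded by CTCAE 4.0 and re-evaluated at each recurrence, and SAP 7.4.1 takes the worst severity per subject. The combined ALT and bilirubin limit triggers an SAE form under Protocol 7.2.6. Grade III and IV hematological toxicity calls for treatment interruption, and interruptions are summarized under SAP 7.4.1 and 7.4.2.

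All of that stands, and it rules out several stronger readings that a reader might infer:

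- That laboratory safety rests on normal/abnormal shifts alone. SAP 7.4.4 itself contradicts this.
- That the laboratory answer depends wholly on investigators choosing to report. For the combined ALT and bilirubin limit, the measured values make reporting mandatory.
- That Protocol 12.3 excludes subjects with an abnormal baseline. It names the normal-to-abnormal case but does not say only that case will be described.
- That the roughly 36 projected transaminase cases would be lost. They are projected from AE counts, and SAP 7.4.1 plans the same kind of analysis.

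It is also fair that table shells are not shown, so finer categories are not ruled out, and that whether a count at the entry limit is abnormal depends on reference ranges the documents do not give. What the reply does not supply is a count of subjects by grade taken from the measurements themselves, which would also serve as a check on AE reporting.

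**Conclusion.** The point holds as a gap in descriptive safety output. As worded, the laboratory shift tables cannot show worsening within the abnormal range, although entry admits abnormal liver tests and SAP section 4 cites CTCAE for laboratory measurements. Such worsening is captured only through summary statistics, the clinical-significance judgement and AE/SAE reporting.

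Its size cannot be fixed from the documents; the ranges in the working rest on an assumed baseline share and assumed independence. The documents do not support a claim that the planned safety tables as a whole would hide a difference between arms. The conclusion is firmest for ALT, AST, bilirubin and creatinine, whose entry limits are written as multiples of the ULN. It is less certain for blood counts, whose normal limits are not stated.

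**What to change.** Keep every output now in SAP 7.4.4. The normal/abnormal shifts should not be replaced, because they are the only tabulation named for urinalysis and stool routine. Add, by arm on the safety set:

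1. A shift table of baseline CTCAE 4.0 grade by worst post-baseline grade, for each gradable hematology and biochemistry parameter.
2. Counts of subjects with ALT > 5 x ULN, with ALT > 8 x ULN, and with ALT > 5 x ULN together with total bilirubin > 2 x ULN. These are the protocol's own limits, used here only as reporting thresholds.

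Extend the laboratory sentence in Protocol 12.3 to cover worsening from any baseline.

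The tests are already scheduled in Protocol 9.2, so the cost is SAP wording and a little programming, assuming each site's reference limits are held in the database. Alpha, power and sample size are unaffected.

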#### **7.4.5 ECG**

ECG: The normal and abnormal changes before and after the treatment based on the normality and abnormality judged by the investigator are described.

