- (7) f: Echocardiography: Must be performed during the screening period. For clinically significant ECG abnormalities observed during the study period, an additional echocardiography examination is required.
- (8) g: ECG: The QTc interval must be indicated for 3 times, with about 5 min apart. ECG examination shall be carried out before drug administration during the screening period and then always after drug administration in each visit. For clinically significant ECG abnormalities, an additional echocardiography examination is required; if there are symptoms such as precordial pain and palpitations, the myocardial zymogram (creatinine kinase, lactate dehydrogenase) should be tested immediately. The examination should be carried out every two cycles after Cycle 3.
- (9) h: Quality of life score: Must be measured before the efficacy evaluation; and measured every two cycles after Cycle 3.
- (10) i: Imaging examination: Screening period: including CT or MRI of the chest and abdomen. Brain CT/MRI is required for clinically suspected metastases to the central nervous system. A bone scan is required for clinically suspected bone metastasis. Treatment period: The examination should be carried out in Cycles 2 and 3, and then every two cycles after Cycle 3.
- (11) i: Efficacy evaluation: The first efficacy evaluation is carried out at the end of Cycle 2; efficacy confirmation is carried out at 4 weeks after the first efficacy evaluation (i.e., at the end of Cycle 3). Afterwards, the efficacy evaluation is carried out every two cycles; For subjects who withdraw from the study due to unacceptable toxicity, the efficacy evaluation should be conducted upon withdrawal if the efficacy evaluation is not carried out within 4 weeks before withdrawal. Thereafter, the imaging examination is performed every 2 cycles until progressive disease.
- (12) Follow-up 1 (can be repeated for V101): The subjects who withdraw from the study due to unacceptable toxicity should be followed-up for tumor progression until the tumor progression is confirmed by imaging or the start of new anti-tumor treatment.
- (13) Follow-up 2 (can be repeated for V201): Survival follow-up, visit number from 201, 202, 203...

REGULATIONS FOR DOSE MODIFICATION

NCI Toxicity Grade	Regulations for Dose Modification	Regulations for Toxicity Recovery upon Re-Administration after Treatment Discontinuation	Regulations for Toxicity Recovery at the Beginning of Next Cycle

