9.2 Treatment Period

- Check the blood pressure once a week post-administration. If the blood pressure is abnormal, follow up with the blood pressure every day, and check the blood pressure three times a week for two cycles after the blood pressure returns to normal, and once a week thereafter.
- Within the first two cycles of administration, carry out the following examinations every two weeks (± 3 days, except for statutory holidays): hematology, urinalysis (not required for female subjects during their menstrual period), hepatic and renal function, and electrolytes. From Cycle 3, the examination is carried out once only at the end of each cycle (± 3 days, except for statutory holidays).
- Within the first three cycles of administration, a 12-Lead ECG is carried out at the end of each cycle (± 3 days, except for statutory holidays), and then carried out at the end of every two cycles (± 7 days, except for statutory holidays). Each examination is carried out after administration for 3 times with about 5 min apart and QTc interval indicated. If there are symptoms such as precordial pain and palpitations, the myocardial zymogram (creatinine kinase, lactate dehydrogenase) should be tested immediately, and ECG should be performed at any time. For clinically significant ECG abnormalities, echocardiography (LVEF) should be performed.
- Physical examination, vital signs, PS score, and coagulation function tests are performed every cycle (± 3 days, except for statutory holidays).
- CT or MRI examination and objective efficacy evaluation of tumor are performed once at the end of every two cycles (± 7 days, except for statutory holidays). If the efficacy reaches CR, PR or SD, the subject must be reexamined 4 weeks after the first evaluation.

Note: For subjects who withdraw from the trial due to unacceptable toxicity, the efficacy evaluation should be conducted upon withdrawal if the efficacy evaluation is not carried out within 4 weeks before withdrawal. Thereafter, the imaging examination is performed at the same frequency, i.e., every 2 cycles until PD or use of other anti-tumor treatments. The radiographic evidence of PD of these subjects must be obtained.

- The quality of life score must be evaluated before each objective efficacy evaluation of tumor.
- Serum AFP is tested once at the end of Cycle 2 (± 7 days, except for statutory holidays) and at the end of Cycle 5 (± 7 days, except for statutory holidays). There is no strict requirement after Cycle 5.

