#### **4.3 Laboratory Tests**

- Hematology: including hemoglobin (HB), red blood cell count (RBC), white blood cell count (WBC), absolute neutrophil count (ANC), neutrophil ratio (N), lymphocyte ratio (Lym), monocyte ratio (Mon), and platelet count (PLT);
- Urinalysis: including urine protein (PRO), urine red blood cells (RBC), and urine white blood cells (WBC);
- Stool routine: occult blood;
- Liver and kidney functions: including total bilirubin (Tbil), direct bilirubin (dBiL), indirect bilirubin (iBiL), alanine aminotransferase (ALT), aspartate aminotransferase (AST), alkaline phosphatase (ALP), Gamma-glutamyltransferase (GGT), lactate dehydrogenase (LDH), total protein (TP), albumin (ALB), creatinine (Cr), urea nitrogen (BUN), and uric acid (UA);

- Electrolytes: potassium ion ( $K^+$ ), sodium ion ( $Na^+$ ), chloride ion ( $Cl^-$ ), calcium ion ( $Ca^{2+}$ ), and blood phosphorus (P); Coagulation function: prothrombin time (PT), activated partial thromboplastin time (APTT), thrombin time (TT), plasma fibrinogen (Fbg), and international normalized ratio (INR);
- 12-Lead ECG: QTc value, heart rate, QTcF, and ECG description.

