## 7.4 Safety Evaluation

### 7.4.1 Adverse events

AEs are encoded according to the current MedDRA 21.0 and then processed in statistical analysis.

The incidences of AEs, treatment-related adverse events (TRAEs), AEs leading to drug interruption, dose reduction, and drug discontinuation, and SAEs are summarized. If multiple AEs occurred in the same subject, the number of subject is counted as one when calculating the incidence; if a subject experiences multiple times of a same AE, the number of subject is counted as one when calculating the incidence of the AE.

AEs are summarized in the frequency table based on SOC and PT. The incidence is calculated based on SOC and symptom/sign (the number of cases is counted as number of subjects who have experienced at least one AE).

Severity of AEs and treatment-related adverse events: If a subject experiences multiple times of the same AE, the most severe one will be used in the analysis of the severity of the AE.

A list of cases of AEs and SAEs is provided.

The median time to the onset of the first event is calculated for the adverse events of special interest (AESIs). AESIs include hypertension, proteinuria, hand-and-foot syndrome, hemorrhage, electrocardiogram QT prolonged, and white blood cell count decreased. The specific classification definitions are shown in Appendix 2.

Time to the onset of first event (days) = onset date of first event – date of the first dose + 1

In addition, for the comparisons of the incidences of AEs between the treatment group and the control group, the Fisher's exact method may be used to calculate the P value, which is only used for clinical reference, rather than the deduction of statistical significance.

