## Appendix 2. Adverse events of special interest

Adverse Event of Special Interest	Preferred Terms of AE
Hypertension	Blood pressure increased
Hypertension	Hypertension
Proteinuria	Protein urine present
Proteinuria	Urine protein
Proteinuria	Proteinuria
Hand-and-Foot Syndrome	Palmar-plantar erythrodysesthesia syndrome
Hemorrhage	Upper gastrointestinal hemorrhage
Hemorrhage	Gastrointestinal hemorrhage
Hemorrhage	Gingival bleeding
Hemorrhage	Anal hemorrhage
Hemorrhage	Hematochezia
Hemorrhage	Melena
Hemorrhage	Mouth hemorrhage

Adverse Event of Special Interest	Preferred Terms of AE
Hemorrhage	Mucosal hemorrhage
Hemorrhage	Subcutaneous hemorrhage
Hemorrhage	Purpura
Hemorrhage	Cerebral hemorrhage
Hemorrhage	Brain stem hemorrhage
Hemorrhage	Pharyngeal hemorrhage
Hemorrhage	Bronchial hemorrhage
Hemorrhage	Hemoptysis
Hemorrhage	Epistaxis
Hemorrhage	Hepatic hemorrhage
Hemorrhage	Scleral hemorrhage
Hemorrhage	Vaginal hemorrhage
Electrocardiogram QT prolonged	QT interval prolonged
White blood cell count decreased	White blood cell count decreased
White blood cell count decreased	Leukopenia

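### SAP 7.4.5 plans no quantitative QTcF analysis: no change from baseline, no count of subjects crossing the protocol's own limits, and no rule for the triplicate readings

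*SAP*

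**What the plan says.** **Collection.** Note g to the protocol's Schedule of Activities states: "The QTc interval must be indicated for 3 times, with about 5 min apart". The screening ECG precedes dosing and later ECGs follow it. Protocol 9.2 repeats this for the treatment period: "Each examination is carried out after administration for 3 times with about 5 min apart and QTc interval indicated". ECGs fall at the end of each of the first three cycles and every two cycles after that.

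**Limits.** Protocol 7.2.5 acts on QTcF. Treatment is interrupted above 480 ms. Resumption depends on a value below 450 ms and within 20 ms of baseline. After re-exposure, a sustained value of 450 to 480 ms, or a rise of more than 20 ms, has dosing consequences.

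**Safety variables.** SAP 4.3 lists "12-Lead ECG: QTc value, heart rate, QTcF, and ECG description". SAP 7.4.1 adds QT to the events of special interest: "AESIs include hypertension, proteinuria, hand-and-foot syndrome, hemorrhage, electrocardiogram QT prolonged, and white blood cell count decreased". Appendix 2 of the SAP feeds that category from one preferred term, "QT interval prolonged".

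**Analysis.** The whole of SAP 7.4.5 reads: "ECG: The normal and abnormal changes before and after the treatment based on the normality and abnormality judged by the investigator are described". By contrast, SAP 7.4.3 (vital signs) and 7.4.4 (hematology, biochemistry, AFP) ask for numeric summaries of values and of changes.

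**The concern.** The trial measures a continuous quantity three times per session, under double-blind placebo control, and sets clinical limits on it. The analysis section then names only a two-level overall judgement. That judgement loses information in three ways.

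- It covers the whole tracing, so rate, conduction and repolarisation findings are mixed with QT.
- A subject already called abnormal for any reason stays abnormal to abnormal, even if QTcF later passes 480 ms.
- A rise of more than 20 ms that stays under 450 ms may leave the call at normal to normal.

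At stake is the size of any QTcF shift relative to placebo, and the number of subjects per arm who crossed the limits the protocol thought worth acting on. Protocol 8.1.2 itself warns that this drug class may prolong QT. The primary overall survival analysis is not affected.

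**Working it through.** The plan gives no figure to reproduce here. The check sets the relevant sections side by side and then illustrates what is forgone.

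**1. What each planned output would show about QTcF**

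| Output | Shift in mean QTcF | Subjects above 480 ms | Use of three readings |
|---|---|---|---|
| SAP 7.4.5, investigator call | no | no | not stated |
| SAP 7.4.1, adverse events | no | only if reported under the QT term | not applicable |
| SAP 7.4.2, interruptions and dose changes | no | indirectly, as interruptions without the QTcF value | not applicable |
| Protocol 12.3 and SAP 7.1, generic rules for continuous data | arguably | no | last value only at baseline |

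The last row needs care. Protocol 12.3 describes visit measurements by mean and SD or by median, with paired tests within arms and ANOVA or rank-sum tests on changes. SAP 7.1 lists summary statistics, and 7.1.3 defines change from baseline. None of these gives threshold counts. Both documents define baseline as the last value before the first dose. Applied literally to a triplicate, that keeps one reading and drops two. Nothing says which on-treatment reading represents the visit.

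**2. Precision a numeric analysis would have (illustration)**

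Inputs: 390 subjects randomised 2:1 (Protocol 4.1), so 390 × 2/3 = 260 and 390 × 1/3 = 130. The SD of QTcF change is not in the documents; 15, 20 and 25 ms are assumed.

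Half-width of the 95% interval for the arm difference = 1.96 × SD × √(1/n₁ + 1/n₂).

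- All subjects contribute (260 and 130): √(1/260 + 1/130) = 0.1074, giving **3.2, 4.2 and 5.3 ms**.
- Half contribute (130 and 65): √(1/130 + 1/65) = 0.1519, giving **4.5, 6.0 and 7.4 ms**.

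Power to detect a 10 ms difference at two-sided 0.05 would be above 0.99, 0.996 and 0.96 with all subjects, and 0.99, 0.91 and 0.75 with half.

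**3. Sensitivity of the adverse-event route (illustration)**

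SAP 7.4.1 allows Fisher's exact test for reference only. Exact power at 260 versus 130, two-sided 0.05, with assumed reporting rates:

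| Placebo | Apatinib | Power |
|---|---|---|
| 1% | 3% | 0.12 |
| 1% | 5% | 0.50 |
| 2% | 6% | 0.39 |
| 2% | 10% | 0.88 |

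The two sets of figures answer different questions, because no assumption here links a mean shift to an event rate. They show that the adverse-event route is insensitive to modest excesses, and no adverse-event table estimates a shift in milliseconds.

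**The case against.** The strongest reply is that QT is far from ignored.

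- **Adverse events.** SAP 7.4.1 states "AEs are summarized in the frequency table based on SOC and PT", so QT prolongation is counted by arm. It is also analysed by worst severity and time to first onset, and may be compared by Fisher's exact test. This stands. A reader might infer that the trial cannot show whether apatinib prolongs QT; the documents do not support that.
- **Interruptions.** Under Protocol 7.2.5 a QTcF above 480 ms leads to interruption, notification and repeat ECGs, and SAP 7.4.1 and 7.4.2 summarise interruptions. So it would be wrong to infer that crossings of 480 ms leave no trace. However, the trace carries no QTcF value. The 450 ms and 20 ms limits apply only to resumption or re-exposure, so a first rise that stays at or below 480 ms triggers nothing under 7.2.5.
- **Generic rules.** Protocol 12.3 and SAP 7.1 can be read to cover a mean QTcF summary, and 7.4.5 does not forbid one. This stands in part. They still give neither threshold counts nor a triplicate rule, and the explicit numeric wording in 7.4.3 and 7.4.4 makes its absence from 7.4.5 look deliberate.
- **Nothing is lost for good.** QTc and QTcF are listed safety variables, so tables could be added at reporting. That is fair, but choices about averaging, baseline and cut-offs would then be made after unblinding.
- **Standing of the AESI.** QT is named as an event of special interest only in the SAP; the protocol's examples are hypertension, proteinuria and hand-and-foot syndrome. The protocol nevertheless gives QTcF its own discontinuation section.

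**Conclusion.** The point holds as a gap in pre-specification. SAP 7.4.5 commits only to the investigator's overall call. The size of any QTcF effect and the number of subjects crossing the Protocol 7.2.5 limits are not planned outputs. What remains (investigator calls, reported events and interruptions) could reveal a large excess but measures the size of an effect poorly.

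Under the assumed SD of 15 to 25 ms, the data could support an arm comparison with a half-width of about 3.2 to 5.3 ms at 260 versus 130, wider if fewer subjects have post-baseline ECGs. That range rests on the SD assumption and on each subject contributing one change value at a common time. The adverse-event power figures rest on assumed reporting rates.

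The point does not support saying that QT prolongation could not be detected, or that the data would be lost. It should be corrected before database lock, but it bears on safety description and not on the efficacy conclusion.

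**What to change.** Rewrite SAP 7.4.5 to specify:

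1. The mean of the three QTcF readings as the value at baseline and at each visit, overriding the last-value baseline rule for ECG.
2. QTcF value and change from baseline summarised by arm and visit, with the number of subjects contributing.
3. By arm and by sex, the maximum post-baseline QTcF (≤ 450, > 450 to 480, > 480 ms) and the number with a maximum increase > 20 ms. The split by sex is warranted because the QTc limits in exclusion criterion 6 differ (450 ms in males, 470 ms in females). State whether repeat ECGs taken under 7.2.5 count towards the maximum.
4. The investigator's call kept as a supporting shift table or listing, with the individual readings listed, since an average can fall below 480 ms when one reading exceeded it.

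The cut-offs are those already in Protocol 7.2.5, used here only to tabulate; no clinical rule changes. Because a maximum tends to grow with the number of ECGs, the maxima should be read beside the by-visit table if treatment duration differs between arms.

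The cost is one SAP paragraph and two or three descriptive tables, with no added visits or procedures. This assumes that the database holds all three readings, which the documents do not state and which should be confirmed first.
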